8.3.2. Reporting

Every SAE, regardless of suspected causality (eg, relationship to study drug(s) or study procedure or disease progression), occurring after the subject has signed the ICF through the last study visit (or 60 days after the last dose of study drug, whichever is later) must be reported to the sponsor (or designee) within **24 hours** of learning of its occurrence, unless otherwise specified by the Protocol. Any SAEs occurring more than 60 days after the last dose of study drug should be reported to the sponsor or its designee only if the investigator suspects a causal relationship to the study drug.

Information about all SAEs is collected and recorded on the Adverse Event form of the eCRF. The investigator must assess and record the causal relationship of each SAE to the study treatment.

The investigator must also complete the Incyte Serious Adverse Event Report Form, in English, and send the completed and signed form to the sponsor or designee within 24 hours of becoming aware of the SAE. The investigator must provide a causality assessment, that is, assess whether there is at least a reasonable possibility that the SAE is related to the study treatment: suspected (yes) or not suspected (no). Refer to the Incyte Reference Guide for Completing the Serious Adverse Event Report Form.

The contact information of the sponsor's study-specific representatives is listed in the investigator manual provided to each site. The original copy of the SAE Report Form and the confirmation sheet must be kept at the study site.

Investigational site personnel must report any new information regarding the SAE within 24 hours of becoming aware of the information in the same manner that the initial SAE Report Form was sent. Follow-up information is recorded on an amended or new SAE Report Form, with an indication that it is follow-up to the previously reported SAE and the date of the original report. The follow-up report should include information that was not provided on the previous SAE Report Form, such as the outcome of the event (eg, resolved or ongoing), treatment provided, action taken with study drug because of the SAE (eg, dose reduced, interrupted, or discontinued), or subject disposition (eg, continued or withdrew from study participation). Each recurrence, complication, or progression of the original event should be reported as follow-up to that event, regardless of when it occurs.

If the SAE is not documented in the IB for the study drug (new occurrence) and is thought to be related to the sponsor's study drug, the sponsor or its designee may urgently require further information from the investigator for reporting to health authorities. The sponsor or its designee may need to issue an Investigator Notification (IN) to inform all investigators involved in any study with the same drug that this SAE has been reported. Suspected Unexpected Serious Adverse Reactions (SUSARs) will be collected and reported to the competent authorities and

relevant ethics committees in accordance with Directive 2001/20/EC, or as per national regulatory requirements in participating countries.

8.4. Emergency Unblinding of Treatment Assignment

Not applicable.

8.5. Pregnancy

Pregnancy, in and of itself, is not regarded as an AE unless there is suspicion that study drug may have interfered with the effectiveness of a contraceptive medication or method. When a pregnancy has been confirmed in a subject during maternal or paternal exposure to study drug, a) within 60 days of the last dose of study drug for maternal exposure, b) within 90 days of the last dose for paternal exposure, or c) within 30 days after cessation of treatment if the subject initiates new anticancer therapy, the following procedures should be followed in order to ensure subject safety:

- The study drug must be discontinued immediately (female subjects only).
- The investigator must complete and submit the Incyte Clinical Trial Pregnancy form to the sponsor or its designee within **24 hours** of learning of the pregnancy.
- A serum pregnancy test must be performed to confirm the urine pregnancy test result. If a negative serum test does not confirm the urine pregnancy test result, then:
 - The investigator will use his or her expert judgment, based on an assessment of the potential benefit/risk to the subject, to determine whether it is in the subject's best interest to resume study drug and continue participation in the study.
- The EOT visit evaluations must be performed.

Data on fetal outcome and breastfeeding are collected for regulatory reporting and drug safety evaluation. Follow-up should be conducted for each pregnancy to determine outcome, including spontaneous or voluntary termination, details of the birth, and the presence or absence of any birth defects, congenital abnormalities, or maternal and/or newborn complications, by following until the first well-baby visit. Pregnancy should be recorded on a Clinical Trial Pregnancy form and reported by the investigator to the sponsor or its designee. Pregnancy follow-up information should be recorded on the same form and should include an assessment of the possible causal relationship to the sponsor's study drug to any pregnancy outcome, as well as follow-up to the first well-baby visit or the duration specified in local regulations, whichever is later. Refer to the Incyte Reference Guide for Completing the Clinical Trial Pregnancy Form.

Any SAE occurring during pregnancy must be recorded on the SAE report form and submitted to the sponsor or designee.

8.6. Warnings and Precautions

Special warnings or precautions for the study drug, derived from safety information collected by the sponsor or its designee, are presented in the Investigator's Brochure (IB). Additional safety information collected between IB updates will be communicated in the form of Investigator Notifications (INs). Any important new safety information should be discussed with the subject

during the study, as necessary. If new significant risks are identified, they will be added to the ICF.

8.7. Data Monitoring Committee

There will be no formal Data Monitoring Committee for this open-label study. For Part 1, the sponsor will conduct telephone conferences with investigators in order to review cohort-specific data, to review overall safety data from previous cohorts (if applicable), and to agree on dose escalation, de-escalation, and cohort expansion decisions on a regular basis (ie, approximately weekly). For Part 2, safety and tolerability will be carefully monitored throughout the study by the sponsor on a regular basis (ie, approximately monthly).

8.8. Immune-Related Adverse Events

Adverse events of a potential immunologic etiology or irAEs may be defined as an AE consistent with an immune phenomenon associated with drug exposure after all other etiologies have been eliminated. Immune-related AEs may be expected based on the nature of INCAGN01949, its mechanism of action, and reported experience with other immunotherapies. Special attention should be paid to AEs that may be suggestive of potential irAEs. An irAE can occur shortly after the first dose or several months after the last dose of treatment. Guidance for the assessment, diagnosis, and management of irAEs is provided in [Section 5.4.7](#) and [Appendix B](#). Suspected irAEs should be discussed with the medical monitor when possible.

8.9. Product Complaints

The sponsor collects product complaints on study drugs and drug delivery systems used in clinical studies in order to ensure the safety of study participants, monitor quality, and facilitate process and product improvements.

All product complaints associated with material packaged, labeled, and released by the sponsor or its designee will be reported to the sponsor. All product complaints associated with other study material will be reported directly to the respective manufacturer.

The investigator or his/her designee is responsible for reporting a complete description of the product complaint via email or other written communication to the sponsor contact or respective manufacturer as noted in the packaging information. Any AE associated with a product complaint should be reported as described in [Section 8.1.2](#) of this Protocol.

If the investigator is asked to return the product for investigation, he/she will return a copy of the product complaint communication with the product.

9. STATISTICS

9.1. Study Populations

The full analysis set/safety population includes all subjects enrolled in the study who received at least 1 dose of study drug (INCAGN01949). They will be used in the analyses of demographic, baseline, safety, study drug administration, and efficacy data.

The PK [REDACTED] evaluable population includes subjects having received at least 1 dose of study drug and had at least 1 PK [REDACTED] sample collected and analyzed.

9.2. Selection of Sample Size

9.2.1. Sample Size in Part 1

The primary objective of Part 1 of the study is to determine the PAD or the MTD of INCAGN01949. The total number of subjects will depend on the number of dose levels tested before the PAD or MTD is established. Approximately 18 to 42 subjects (6 subjects per dose level for 7 dose levels) will be included based on the dose escalation. Dose escalation will follow the 3 + 3 design algorithm. Based on this algorithm, a minimum of 3 evaluable subjects will be enrolled in each cohort beginning with Cohort 1 (7 mg; starting dose) and a maximum of 6 subjects for each cohort.

Part 1 of the study may also include safety expansion cohorts evaluating dose(s) and schedule(s) equivalent to or lower than the highest dose levels determined to be safe and/or doses determined to be pharmacologically active. Each safety expansion cohort will enroll 9 evaluable subjects. Up to 36 subjects will be enrolled in Part 1 safety expansion. If < 3 of 9 evaluable subjects experience a DLT, then the cohort will be deemed safe. If more than 1 safety expansion cohort is deemed safe, then a recommended dose and schedule will be determined in conjunction with the investigators and sponsor based on all available safety, PK, [REDACTED] results.

9.2.2. Sample Size in Part 2

Part 2 of the study will further evaluate the safety, tolerability, preliminary efficacy, PK, and pharmacologic activity of the recommended dose of INCAGN01949. The sample size for each tumor type will be guided by the Simon 2-stage design (Simon 1989). Let 5% be a clinically insignificant response rate for all tumor types. During Stage 1, 9 subjects will be enrolled; if no responses are observed, then the cohort will be discontinued. If at least 1 response is observed, then 8 additional subjects will be enrolled (Stage 2), for a maximum of 17 subjects per tumor type in Part 2. The detailed calculation is based on a 1-sided Type I error of 0.05 and power of 80% to detect a 25% response rate for each of the tumor types.

9.3. Level of Significance

For the primary efficacy endpoints of objective response rate, the 1-sided Type I error will be controlled at 0.05 for each individual cohort expansion. Note that this level of significance does not account for the multiple expansion cohorts. For other endpoints, confidence intervals will be reported at a 95% confidence level.

9.4. Statistical Analyses

9.4.1. Efficacy Analyses

9.4.1.1. Primary Efficacy Analyses

In Part 2, the proportion of subjects who meet the objective response criteria (CR + PR) per mRECIST v1.1 will be summarized by tumor type.

If there are no responses with each tumor type out of 9 subjects (consistent with a calculated response rate < 5%) at Stage 1, then the study will be stopped for futility, and the null hypothesis is not rejected. Otherwise, in the tumor types in which at least 1 response among the Stage 1 subjects is observed, 8 additional subjects will be treated in Stage 2. If there are ≤ 2 responders among 17 subjects at the end of Stage 2, then the drug will be declared nonpromising for that tumor type, and the null hypothesis is not rejected. Further investigation of the study drug will be considered interesting (predictive of $\geq 25\%$ response rate) if ≥ 3 responses are observed in the first 17 subjects. For the hypothesis test in the Simon 2-stage design, the null response rate is 5% and alternative response rate is 25%.

9.4.1.2. Secondary Efficacy Analyses

The PK of INCAGN01949 will be summarized.

The proportion of subjects who have disease control (CR + PR + SD), as per RECIST v1.1 and mRECIST v1.1 will be summarized.

Progression-free survival and duration of response will be estimated using the Kaplan-Meier method as per RECIST v1.1 and mRECIST v1.1.

9.4.2. Safety Analyses

9.4.2.1. Adverse Events

A treatment-emergent adverse event (TEAE) is any AE either reported for the first time or worsening of a pre-existing event after the first dose of study drug. Analysis of AEs will be limited to TEAEs, but data listings will include all AEs regardless of their timing in relation to study drug administration. Adverse events will be tabulated by the MedDRA preferred term and system organ class. Severity of AEs will be based on the NCI CTCAE v4.03 using Grades 1 through 4.

The subset of AEs considered by the investigator to have a relationship to study drug will be considered to be treatment-related AEs. If the investigator does not specify the relationship of the AE to study drug, then the AE will be considered treatment-related. The incidence of AEs and treatment-related AEs will be tabulated.

9.4.2.2. Clinical Laboratory Tests

Laboratory test values outside of the normal range will be assessed for severity based on the normal ranges for the clinical reference laboratory. The incidence of abnormal laboratory values and shift tables relative to baseline will be tabulated.

Laboratory data will be classified into Grades 1 through 4 using CTCAE v4.03. The following summaries will be produced for the laboratory data:

- Number and percentage of subjects with worst postbaseline CTCAE grade (regardless of baseline value). Each subject will be counted only for the worst grade observed postbaseline.
- Shift tables from baseline to the worst postbaseline value using CTCAE grade.
- For laboratory parameters where CTCAE grades are not defined, shift tables to the worst postbaseline value using the low/normal/high classifications based on laboratory reference ranges.

9.4.2.3. Vital Signs

Descriptive statistics and mean change from baseline will be determined for vital signs (blood pressure, pulse, respiratory rate, and body temperature) at each assessment time. Vital sign results will be reviewed for clinically notable abnormalities (see [Table 15](#)), and subjects exhibiting clinically notable vital sign abnormalities will be listed. A value will be considered an "alert" value if it is outside the established range and shows a > 25% change from baseline.

Table 15: Criteria for Clinically Notable Vital Sign Abnormalities

Parameter	High Threshold	Low Threshold
Systolic blood pressure	> 155 mmHg	< 85 mmHg
Diastolic blood pressure	> 100 mmHg	< 40 mmHg
Pulse	> 100 bpm	< 45 bpm
Temperature	> 38°C	< 35.5°C
Respiratory rate	> 24/min	< 8/min

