Note: Subjects with hyper/hypothyroidism are eligible to participate.
Note: Replacement and symptomatic therapies (eg, levothyroxine, insulin, or physiologic corticosteroid replacement therapy for adrenal or pituitary insufficiency, etc) are not considered a form of systemic treatment and are allowed.
7. Known active CNS metastases and/or carcinomatous meningitis.
Note: Subjects with previously treated brain metastases may participate provided that they are stable (without evidence of progression by imaging for at least 28 days before the first dose of study drug and any neurologic symptoms have returned to baseline), have no evidence of new or enlarging brain metastases or CNS edema, and have not required steroids for at least 14 days before the first dose of study drug.
8. Known additional malignancy that is progressing or requires active treatment, or history of other malignancy within 2 years of study entry with the exception of cured basal cell or squamous cell carcinoma of the skin, superficial bladder cancer, prostate intraepithelial neoplasm, carcinoma *in situ* of the cervix, or other noninvasive or indolent malignancy, or cancers from which the subject has been disease-free for > 1 year, after treatment with curative intent.
9. Evidence of active, noninfectious pneumonitis or history of interstitial lung disease.
10. History or presence of an abnormal ECG that, in the investigator's opinion, is clinically meaningful. Screening QTc interval > 470 milliseconds is excluded (corrected by Fridericia). In the event that a single QTc is > 470 milliseconds, the subject may enroll if the average QTc for the 3 ECGs is < 470 milliseconds. For subjects with an intraventricular conduction delay (QRS interval > 120 milliseconds), the JTc interval may be used in place of the QTc with sponsor approval. The JTc must be < 340 milliseconds if JTc is used in place of the QTc. Subjects with left bundle branch block are excluded.
Note: QTc prolongation due to pacemaker may enroll if the JTc is normal or with medical monitor approval.
11. Active infection requiring systemic therapy.

12. Evidence of hepatitis B virus (HBV) or hepatitis C virus (HCV) infection or risk of reactivation. Hepatitis B virus DNA and HCV RNA must be undetectable. Subjects cannot be positive for HBV DNA, HCV RNA, hepatitis B surface antigen, or anti-hepatitis B core antibody, without approval from the medical monitor.

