8.4. Vital Signs

Values at each scheduled visit, change, and percentage change from baseline for vital signs, including systolic blood pressure, diastolic blood pressure, pulse, respiratory rate, body temperature, and weight will be summarized descriptively. Change and percentage change from baseline will be calculated using the last nonmissing value before first dose of study drug (Day 1) as the baseline value.

Criteria for clinically notable vital sign abnormalities are defined in [Table 6](#). The abnormal values for subjects exhibiting clinically notable vital sign abnormalities will be listed along with their assigned treatment group. Alert vital signs are defined as an absolute value outside the defined range and percentage change $> 25\%$. The abnormal values for subjects exhibiting alert vital sign abnormalities will be listed.

Table 6: Criteria for Clinically Notable Vital Sign Abnormalities

Parameter	High Threshold	Low Threshold
Systolic blood pressure	> 155 mmHg	< 85 mmHg
Diastolic blood pressure	> 100 mmHg	< 40 mmHg
Pulse	> 100 bpm	< 45 bpm
Temperature	> 38°C	< 35.5°C
Respiratory rate	> 24/min	< 8/min

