8.5. Electrocardiograms

Timed triplicate ECGs (separated by 5 minutes) will be conducted at screening and in conjunction with the pre- and postinfusion PK timepoints on C1D1 and C6D1. The baseline ECG measurement will be the average of the 3 nonmissing triplicate ECGs performed preinfusion on C1D1.

Singleton 12-lead ECGs including heart rate, PR, QRS, QT, RR, QTcF, and JTC intervals (where applicable) will be obtained for each subject on Day 1 of every other cycle after Cycle 2 (eg, Cycle 4, Cycle 6, Cycle 8, Cycle 10, etc) during the study. Values at each scheduled visit, change, and percentage change from baseline will be summarized for each ECG parameter. Separate summaries will be provided for triplicate ECGs and singleton 12-lead ECGs.

Criteria for clinically notable ECG abnormalities are defined in [Table 7](#). Subjects exhibiting clinically notable ECG abnormalities will be listed with study visit and assigned treatment group. Abnormal values for subjects with alert ECG values, defined as both the absolute value and the percentage change from baseline being outside normal ranges, will be identified and listed.

Table 7: Criteria for Clinically Notable Electrocardiogram Abnormalities

Parameter	High Threshold	Low Threshold
QTcF	> 460 msec	< 295 msec
PR	> 220 msec	< 75 msec
QRS	> 120 msec	< 50 msec
QT	> 500 msec	< 300 msec
RR	> 1330 msec	< 600 msec

QTcF = Fridericia correction.

Electrocardiogram abnormalities, both at baseline and postbaseline visits, will be tabulated by treatment group. Incidences of abnormalities will be listed separately for triplicate and singleton ECGs with study visit, assigned treatment group, and a description of the abnormality.

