Note 2: normal range for Respiratory Rate is 8 - 24 breaths/min. Alert values are defined as the measured value being outside the normal range and the percent change from baseline being > 25%.

Reference: Listings 2.8.XX

PROTOCOL: INCAGN 1949-101
DRUG/INDICATION: OX40/Advanced or Metastatic Solid Tumors
TLF VERSION: Draft

(Page n of N)
DATABASE VERSION: XXXXX

Table 3.4.5.1

Summary of Body Temperature (°C)
(Population: Part 1 FAS Population)

Dose Level (mg/kg) :Dose 1

This table follows same shell as that for 3.4.1.1

FOLDER\PROGRAM\OUTPUT: XXXXXX\XXXXXX.SAS\XXXXXX.LST

DATE (TIME): MMDDYYYY (hh:mm)

Note 1: Baseline is the last value collected before the first dose of study drug.

Note 2: The normal range for Body Temperature is 35.5 - 38 C. Alert values are defined as the measured value being outside the normal range and the percent change from baseline being > 25%.

Reference: Listings 2.8.XX

PROTOCOL: INCAGN 1949-101
DRUG/INDICATION: OX40/Advanced or Metastatic Solid Tumors
TLF VERSION: Draft

(Page n of N)
DATABASE VERSION: XXXXX2016

Table 3.4.5.2

Summary of Body Temperature (°C)
(Population: Part 2 FAS Population)

Cancer Type :Endometrium

This table follows same shell as that for 3.4.1.2

FOLDER\PROGRAM\OUTPUT: XXXXXX\XXXXXX.SAS\XXXXXX.LST

DATE (TIME): MMDDYYYY (hh:mm)

Note 1: Baseline is the last value collected before the first dose of study drug.

Note 2: The normal range for Body Temperature is 35.5 - 38 C. Alert values are defined as the measured value being outside the normal range and the percent change from baseline being > 25%.

Reference: Listings 2.8.XX

PROTOCOL: INCAGN 1949-101
DRUG/INDICATION: OX40/Advanced or Metastatic Solid Tumors
TLF VERSION: Draft

(Page n of N)
DATABASE VERSION: XXXXX

Table 3.4.6.1
Summary of Body Weight (kg)
(Population: Part 1 FAS Population)

Dose Level (mg/kg)	Visit	Descriptive Summary				
		N	Mean	STD	Min	Median
Dose 1	Baseline	xxx	x.xxxxx	x.xxxxxx	x.xxxx	x.xxxxx x.xxxx
	Cycle 2	xxx	x.xxxxx	x.xxxxxx	x.xxxx	x.xxxxx x.xxxx
	Change from Baseline	xxx	x.xxxxx	x.xxxxxx	x.xxxx	x.xxxxx x.xxxx
	% Change from Baseline	xxx	x.xxxxx	x.xxxxxx	x.xxxx	x.xxxxx x.xxxx
	Cycle 3	xxx	x.xxxxx	x.xxxxxx	x.xxxx	x.xxxxx x.xxxx
	Change from Baseline	xxx	x.xxxxx	x.xxxxxx	x.xxxx	x.xxxxx x.xxxx
	% Change from Baseline	xxx	x.xxxxx	x.xxxxxx	x.xxxx	x.xxxxx x.xxxx
	Cycle 4	xxx	x.xxxxx	x.xxxxxx	x.xxxx	x.xxxxx x.xxxx
	Change from Baseline	xxx	x.xxxxx	x.xxxxxx	x.xxxx	x.xxxxx x.xxxx

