Week xx	Measured	xxx	xxx.x	xxx.x	xxx.x	xxx.x	xxx.x	xxx.x	xxx	xx.x	xxx	xx.x	xxx	xx.x	xxx	xx.x
	Change	xxx	xxx.x	xxx.x	xxx.x	xxx.x	xxx.x	xxx.x	xxx	xx.x	xxx	xx.x	xxx	xx.x	xxx	xx.x
	% Change	xxx	xxx.x	xxx.x	xxx.x	xxx.x	xxx.x	xxx.x	xxx	xx.x	xxx	xx.x	xxx	xx.x	xxx	xx.x

FOLDER\PROGRAM\OUTPUT: XXXXXX\XXXXXX.SAS\XXXXXX.LST

DATE (TIME) : MMDDYYYY (hh:mm)

Note 1: Baseline is the average of all measurements collected before the first dose of study drug.

Note 2: The normal range for QTcF is 295 - 460 mm/Hg.

Alert values are defined as the measured value being outside the normal range and the percent change from Baseline being > 25%.

Abbreviation: STD = Standard Deviation; Min = Minimum; Max = Maximum.

Reference: Listings 2.9.4

PROTOCOL: INCAGN 1949-101
DRUG/INDICATION: OX40/Advanced or Metastatic Solid Tumors
TLF VERSION: Draft

(Page n of N)
DATABASE VERSION: XXXXX2016

Table 3.5.5.2

Summary of QTcF Interval (msec) from Central Lab 12-Lead ECG
(Population: Part 2 FAS Population)

Cancer Type : Endometrium

Study Visit	Variable	Descriptive Summary						Low		Normal		High		Alert		
		N	Mean	STD	Min	Median	Max	N	%	N	%	N	%	N	%	
Baseline	Baseline	xxx	xxx.x	xxx.x	xxx.x	xxx.x	xxx.x	xxx.x	xxx	xx.x	xxx	xx.x	xxx	xx.x	xxx	xx.x
Week xx	Measured	xxx	xxx.x	xxx.x	xxx.x	xxx.x	xxx.x	xxx.x	xxx	xx.x	xxx	xx.x	xxx	xx.x	xxx	xx.x
	Change	xxx	xxx.x	xxx.x	xxx.x	xxx.x	xxx.x	xxx.x	xxx	xx.x	xxx	xx.x	xxx	xx.x	xxx	xx.x
	% Change	xxx	xxx.x	xxx.x	xxx.x	xxx.x	xxx.x	xxx.x	xxx	xx.x	xxx	xx.x	xxx	xx.x	xxx	xx.x
Week xx	Measured	xxx	xxx.x	xxx.x	xxx.x	xxx.x	xxx.x	xxx.x	xxx	xx.x	xxx	xx.x	xxx	xx.x	xxx	xx.x
	Change	xxx	xxx.x	xxx.x	xxx.x	xxx.x	xxx.x	xxx.x	xxx	xx.x	xxx	xx.x	xxx	xx.x	xxx	xx.x
	% Change	xxx	xxx.x	xxx.x	xxx.x	xxx.x	xxx.x	xxx.x	xxx	xx.x	xxx	xx.x	xxx	xx.x	xxx	xx.x

FOLDER\PROGRAM\OUTPUT: XXXXXX\XXXXXX.SAS\XXXXXX.LST

DATE (TIME): MMDDYYYY (hh:mm)

Note 1: Baseline is the average of all measurements collected before the first dose of study drug.

Note 2: The normal range for QTcF is 295 - 460 mm/Hg.

Alert values are defined as the measured value being outside the normal range and the percent change from Baseline being > 25%.

Abbreviation: STD = Standard Deviation; Min = Minimum; Max = Maximum.

Reference: Listings 2.9.4

PROTOCOL: INCAGN 1949-101
DRUG/INDICATION: OX40/Advanced or Metastatic Solid Tumors
TLF VERSION: Draft

(Page n of N)
DATABASE VERSION: XXXXX

Table 3.5.6.1

Summary of JTc Interval (msec) from Central Lab 12-Lead ECG
(Population: Part 1 FAS Population)

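### The vital-sign alert rule cannot in practice flag any body temperature, and the SAP's QTcF alert rule is unclear and insensitive; both are reporting flags only

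*Protocol*

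**What the plan says.** **Vital signs.** Protocol Section 9.4.2.3 defines an alert as a value "outside the established range and shows a > 25% change from baseline". Table 15, in the same section, includes temperature (above 38 °C or below 35.5 °C), and no parameter is exempted. SAP Section 8.4 agrees: "Alert vital signs are defined as an absolute value outside the defined range and percentage change" of more than 25%. The shells for Tables 3.4.5.1 and 3.4.5.2 apply this to Celsius readings. Their footnote states "The normal range for Body Temperature is 35.5 - 38 C" and continues "Alert values are defined as the measured value being outside the normal range and the percent change from baseline being > 25" per cent. These shells follow the layout of Table 3.4.1.1, which has Low, Normal, High and Alert columns. Listing 2.8.3 is a separate listing of alert vital signs.

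**ECG.** Protocol Section 9.4.2.4 has no alert rule. SAP Section 8.5 has one, "defined as both the absolute value and the percentage change from baseline being outside normal ranges", but it does not say what percentage counts as outside a normal range. The figure appears only in the Appendix A shells. For QTcF (Tables 3.5.5.1 and 3.5.5.2) the footnote reads "The normal range for QTcF is 295 - 460 mm/Hg", with the unit misprinted, and "Alert values are defined as the measured value being outside the normal range and the percent change from Baseline being > 25" per cent.

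**Displays without a percentage condition.** Both documents list values outside Tables 15 and 16 of the Protocol (Tables 6 and 7 of the SAP). The shells for SAP Tables 3.5.8.1 and 3.5.8.2 count QTcF of at least 450, 480 and 500 ms, and changes of at least 30 and 60 ms.

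**The concern.** A percentage of a Celsius reading depends on where the scale puts its zero, so 25% of it has no physiological meaning. Normal temperature also varies by far less than 25%. A rule that suits pulse therefore becomes unattainable when it is copied to temperature.

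Alert is presented as a tier above High and Low, because it adds a second condition. A zero in that column invites the reading that no serious temperature excursion occurred, when no realistic excursion could have been counted. Temperature is not incidental here. The Protocol discusses cytokine release as a potential risk in its preclinical sections, gives infusion-reaction guidelines (Section 5.4.8), and has temperature taken hourly for 4 hours after the first four infusions (Table 7, footnote c).

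For QTcF the issue is consistency. The alert flag, if programmed from the shells, would disagree with the outlier categories the sponsor chose a few tables later.

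**Working it through.** The plan states no figure for this point, so there is none to reproduce. The check is arithmetic on the rule.

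**Inputs.** The range for temperature is 35.5 to 38 °C and for QTcF 295 to 460 ms (Protocol Tables 15 and 16; SAP shells). The percentage is 25%. Baselines are assumptions, because the documents give no distribution. For temperature I use the stated normal range, 35.5 to 38 °C. For QTcF I use 360 to 470 ms, the upper end reflecting the exclusion of screening QTcF above 470 ms (Protocol Section 3.2). I read percentage change as a change in either direction.

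**Rule.** With baseline b, lower limit L and upper limit U:
- high alert if the value is greater than max(U, 1.25 × b)
- low alert if the value is less than min(L, 0.75 × b)

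**Temperature.** 1.25 × b always exceeds 38 and 0.75 × b is always below 35.5, so the percentage decides every case.

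| Baseline (°C) | High alert above | Low alert below |
|---|---|---|
| 35.5 | 44.4 | 26.6 |
| 36 | 45.0 | 27.0 |
| 37 | 46.25 | 27.75 |
| 38 | 47.5 | 28.5 |

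A reading of 42 °C from 37 °C is 42/37 − 1 = 13.5%, not an alert. It would be one only from a baseline below 42/1.25 = 33.6 °C.

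**Comparison.** The same rule works for other vital signs, where the range limit is often more than 25% from baseline: pulse 70 to 100 is +42.9%, systolic pressure 120 to 155 is +29.2%, respiratory rate 16 to 24 is +50%. For temperature, 37 to 38 is only +2.7%.

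**QTcF, using the shells' 25%.**

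| Baseline (ms) | High alert above (ms) | Rise needed (more than, ms) |
|---|---|---|
| 360 | 460 | 100 |
| 368 | 460 | 92 |
| 380 | 475 | 95 |
| 400 | 500 | 100 |
| 420 | 525 | 105 |
| 440 | 550 | 110 |
| 460 | 575 | 115 |
| 470 | 587.5 | 117.5 |

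- The two conditions meet at b = 460/1.25 = 368 ms. Below that the rise needed is 460 − b, above it 0.25 × b. The minimum is 92 ms, so a rise of 92 ms or less is never a high alert.
- A rise of 60 ms is 60/360 = 16.7% to 60/460 = 13.0%. It would exceed 25% only from a baseline below 60/0.25 = 240 ms.
- A value of 500 ms is +31.6% from 380 ms (flagged), exactly +25.0% from 400 ms (not flagged, since the rule is strict), +19.0% from 420 ms and +13.6% from 440 ms (not flagged).
- A rise from 420 to 510 ms is +21.4%, not an alert. Tables 3.5.8.1 and 3.5.8.2 would count it both as 500 ms or more and as a change of 60 ms or more.

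**The case against.** The best answer is that nothing goes unreported. The temperature shells count every reading above 38 °C as High in the same row as the empty Alert column, and Listing 2.8.2 shows abnormal values. QTcF above 460 ms is listed, and marked prolongation is tabulated in Tables 3.5.8.1 and 3.5.8.2. No dosing or stopping decision uses the alert flag: dose-limiting toxicities and discontinuation rest on CTCAE grade and investigator judgement, and infusion reactions have their own guidelines and Listing 2.6.14. On these facts the fix partly duplicates existing displays.

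All of that stands, and it limits the size of the point. It does not make the Alert column informative, and the overlap can be avoided by marking the temperature alert not applicable.

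It is also fair to say that the QTcF half rests on shells that Appendix A describes as guidelines. A reader might infer from the Protocol wording that a 25% ECG rule is in force. The documents do not support that: the Protocol sentence covers vital signs only, and SAP Section 8.5 leaves the figure open. What stands is that text and shells need reconciling.

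**Conclusion.** For temperature the rule is wrong as written. The alert count and the temperature part of Listing 2.8.3 will be empty by construction. This is a practical certainty, not a mathematical one, and it holds for any baseline in the stated normal range. For QTcF the finding is narrower. The SAP text gives no percentage; the shells' 25% would leave 500 ms unflagged from baselines of 400 ms or more, and a 60 ms rise unflagged at any plausible baseline.

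Two stronger readings are tempting. One is that fevers or QT prolongation would be hidden from the study report. The High columns, the abnormal-value listings and the outlier tables contradict this. The other is that the QTcF alert misses all marked prolongation. It does not: 500 ms from a baseline of 380 ms is flagged.

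The point concerns uninformative reporting flags. It is minor, but cheap to correct.

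**What to change.** **Temperature.** In SAP Section 8.4 and the shells for Tables 3.4.5.1 and 3.4.5.2, remove the percentage condition and define the alert by the Table 15 range alone. If that is judged to repeat the High and Low columns, show the alert as not applicable, with a footnote. Align the sentence in Protocol Section 9.4.2.3, or record the departure in the SAP. Keep the 25% rule for blood pressure, pulse and respiratory rate.

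**QTcF.** State the ECG alert criterion explicitly in SAP Section 8.5 and make the shells match. For QTcF, base the alert flag and listings on categories already in Tables 3.5.8.1 and 3.5.8.2: 500 ms or more, or an increase of 60 ms or more. Correct the unit in the shell footnotes to milliseconds.

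**Cost.** Two flags to reprogram, a few footnotes, a few more listed records, and some overlap with existing displays. No change to data collection or patient management.
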